8.2. Subject Exclusion Criteria

The subjects who meet any of the following criteria will be excluded from the study:

- 1. Subject is at high risk of non-compliance in the opinion of the Investigator.
- 2. Subject plans to initiate treatment with a prohibited psychotropic medication during the study.
- 3. Subject plans to initiate treatment with transcranial magnetic stimulation (TMS), electroconvulsive therapy (ECT), vagus nerve stimulation (VNS), or deep brain stimulation (DBS) during the study.
- 4. Subject experienced a moderate or severe hyperprolactinemia-related AESI in the lead-in study of SEP-4199 CR.
- 5. Subject will require treatment with a drug that is associated with increases in QTc interval (see Section 23, Appendix IV for a list of medications, not all inclusive).
- 6. Subject had any of the following at Visit 6/EOT (Day 42) of the lead-in study of SEP-4199 CR based on machine reading:
 - increase in QTcF interval of ≥ 30 msec from Baseline of the lead-in study of SEP-4199 CR AND a QTcF interval ≥ 480 msec
 - increase in QTcF interval \geq 60 msec from Baseline of the lead-in study of SEP-4199 CR
 - QTcF interval > 500 msec
 - treatment-emergent clinically significant ECG abnormality.

- Subject is considered by the Investigator to be at imminent risk of suicide or injury to self or others, has a MADRS item 10 (suicidal ideation) score ≥ 4, or answers "yes" to "suicidal ideation" item 4 (active suicidal ideation with some intent to act, without specific plan) or item 5 (active suicidal ideation with specific plan and intent) on the C-SSRS assessment at Visit 6/EOT (Day 42) of the lead-in study of SEP-4199 CR.
- 8. Female subject of child-bearing potential has a positive urine pregnancy test at Visit 6/EOT (Day 42) of the lead-in study of SEP-4199 CR or plans to become pregnant during the current study.
- 9. Subject tests positive for any drug of abuse or cannabis at Visit 6/EOT (Day 42) of the lead-in study of SEP-4199 CR.

9. STUDY DRUG MATERIALS AND MANAGEMENT

9.1. Description of Study Drug

SEP-4199 CR will be supplied as 200 mg tablets containing a fixed 85:15 ratio of aramisulpride:esamisulpride.

- For the SEP-4199 CR 200 mg/day dose, study drug will consist of 1 x 200 mg tablet.
- For the SEP-4199 CR 400 mg/day dose, study drug will consist of 2 x 200 mg tablets.

A description of the investigational product is provided in Table 5.

Attribute	Investigational Product
Product name	SEP-4199 CR 200 mg
Dosage form	Tablets
Unit dose	Tablet
Route of administration	Oral
Physical description	Pale orange round film-coated unmarked tablets
Excipients	D-Mannitol, partly pregelatinized starch, partially hydrolyzed polyvinyl alcohol, hypromellose, light anhydrous silicic acid, sodium stearyl fumarate, Macrogol 400, titanium oxide, talc, ferric oxide yellow, red ferric oxide, and carnauba wax

Table 5:Investigational Product

9.2. Study Drug Packaging and Labeling

9.2.1. Package Description

Study drug will be provided in one-week blister cards (7 days + 2 extra days) containing 9 or 18 tablets of SEP-4199 CR 200 mg tablets. The 200 mg blister cards will contain 9 tablets; subjects will be instructed to take a column of one tablet per day, according to dosing instructions. The 400 mg blister cards will contain 18 tablets; subjects will be instructed to take a column of two tablets each day, according to dosing instructions.

9.2.2. Labeling Description

All packaging for the study medications will be labeled with:

- Protocol number
- Sponsor's name and address
- Compound/Code or name of investigational drug and dosage form
- Content (eg, number of tablets)
- Investigational New Drug statement/caution statement
- Instructions for use and storage

- Batch number
- Period of use (as required)
- Blank space to record visit number
- Blank space for subject identifiers
- Unique medication number/kit ID number
- Investigator information (if needed)

9.3. Study Drug Storage

All study drug should be stored at 15°C to 25°C (59°F to 77°F) and away from light. Excursions of 9°C to 30°C (48°F to 86°F) are permitted during shipment of study drug to investigational sites. The subject will be instructed to store the medication at room temperature.

9.4. Dispensing of Study Drug

An Interactive Web Response System (IXRS) will be used to manage subject enrollment. The IXRS is an integrated web-based subject and drug management system.

Study drug blister cards will be assigned by the IXRS based on the treatment schedule. The IXRS will generate instructions for which blister card ID(s) to dispense to a subject. Each subject will be dispensed two or four 9-day (7 days + 2 extra days) blister cards per scheduled visit, depending on the timing of the next scheduled visit (see Table 2).

The first study drug dose will be taken on Day 1. Subjects will take one or two tablets of study drug according to dosing instructions once a day in the morning at approximately the same time each day. Study drug may be taken with or without food.

9.5. Study Drug Accountability

The Investigator or designee is responsible for maintaining adequate and up to date records of drug disposition that includes dates, quantities, and use by subjects.

Upon receipt of study drug, the Investigator or designee will inspect the supplies and verify receipt of the shipment in the IXRS, confirming the date of receipt, inventory, and condition of study drug received.

The IXRS will also be used for the accountability of the study drug at the clinical site. The Investigator or designee will maintain records for accountability within the IXRS, including study drug dispensation, return, and availability of study drug received. The Investigator or designee will collect and document all used and unused study drug from study subjects at appropriate study visits.

9.6. Study Drug Handling and Disposal

The Investigator or designee is responsible for storing the study drug in a secure location. Study drug should be maintained under the strict control of qualified staff at all times. Proper handling and storage guidelines should be followed.

If the study is stopped for any reason or completed, all unused supplies will be returned to the Sponsor, unless other instructions are provided in writing by the Sponsor/contract research organization (CRO).

The Investigator or designee is required to return all used and unused study drug and packaging to the Sponsor or designee as instructed. The Investigator or designee is required to maintain copies of study drug shipping receipts, drug accountability records, and records of return or final disposal of the study drug in accordance with local regulatory requirements.

Study drug will not be dispensed to any person who is not a study subject under this protocol.

10. TREATMENT OF SUBJECTS

10.1. Study Medication

SEP-4199 CR 200 mg tablets for 200 mg and 400 mg doses will be supplied as described in Section 9.1.

Study drug will be self-administered by the subject once daily as a single oral dose in the morning at approximately the same time, beginning on Day 1 and continuing through Visit 14E (Month 12).

10.1.1. Dose Adjustment Criteria

All subjects will initiate treatment with SEP-4199 CR 200 mg/day. The dose may be increased to 400 mg/day at Visit 2E (Week 2/Day 14) or later, based on the Investigator's judgment. However, if clinically indicated, the dose may be increased as early as Day 7 at an unscheduled visit. The decision to increase the dose and dispense additional study drug will be made by the Investigator at a scheduled or unscheduled study visit. A dose decrease can occur at any time for safety or tolerability concerns (minimum dose of 200 mg/day). If a dose decrease is needed between study visits, subjects will return to the clinic for an unscheduled visit for drug dispensation. Temporary interruption of the study drug is allowed at the Investigator's discretion for specific hyperprolactinemia-related AESI (see Section 13.1).

Prior to a dose increase, safety assessments will be completed, including but not limited to evaluation of adverse events, concomitant medications, vital signs, and ECGs. Subjects whose ECG results, based on machine reading, show increase from Baseline in QTcF interval \geq 30 msec or whose QTcF interval is \geq 480 msec at the 200 mg/day dose are not allowed to have their dose increased to 400 mg/day. Subjects with hyperprolactinemia-related AESI are not allowed to have their dose increased to 400 mg/day. IXRS drug dispensing guidelines should be followed for dispensing the drug to subjects. A specific user manual will be provided.

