- Overall bipolar depression severity assessed using the Clinical Global Impression-Bipolar Version-Severity of Illness (CGI-BP-S), Depression scale

- Anxiety symptoms severity assessed using the clinician-administered Hamilton Anxiety Rating Scale (HAM-A)
- Severity of subject-reported depression symptoms as measured by the Quick Inventory of Depressive Symptomatology, Self-Report (QIDS-SR16)
- Functional impairment, as measured by the Sheehan Disability Scale (SDS)
- Quality of life, as measured by the EuroQol 5 Dimension 5 Level (EQ-5D-5L)
- Anhedonia symptoms, as measured by the Snaith-Hamilton Pleasure Scale (SHAPS).

Pharmacokinetics and Pharmacodynamics Objectives:

- Perform population pharmacokinetic (Pop-PK) analysis using plasma SEP-4199 concentrations.
- Explore the relationship between MADRS score and plasma SEP-4199 exposure using population PK/pharmacodynamics (PD) methods.
- Explore the relationship between safety outcomes and plasma SEP-4199 exposure.

Study Design: SEP380-303 is a 12-month open-label safety extension study to evaluate the long-term safety, tolerability, and effectiveness of SEP-4199 CR 200-400 mg/day in the treatment of subjects with bipolar I depression who previously completed a lead-in study of SEP-4199 CR.

The study will consist of a 12-month open-label flexible-dose treatment period, and a safety follow-up period, as shown in the following figure. There are 15 scheduled visits including a Baseline visit, 13 visits during the open-label treatment period, and 1 safety follow-up visit 7 (\pm 2) days after the last dose of study drug. If necessary, subjects may return to the clinic at any time for an unscheduled visit.

Baseline (Visit 1E; Day -1)

Visit 6/End of Treatment (EOT) (Day 42) of the lead-in study of SEP-4199 CR will serve as the Baseline visit of the current open-label extension study. Subjects who completed 6 weeks of double-blind treatment in a lead-in study of SEP-4199 CR and who meet eligibility criteria to continue into the current extension study may be enrolled. Baseline values for safety and effectiveness measures for this study will be carried over from Visit 6/EOT (Day 42) of the lead-in study of SEP-4199 CR for each subject. Subjects should continue dosing with SEP-4199 CR in the current open-label study without dosing interruption.

Open-Label Treatment Period (Day 1 to Visit 14E/Month 12)

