7. INVESTIGATIONAL PLAN

7.1. Overall Study Design

SEP380-303 is a 12-month open-label safety extension study to evaluate the long-term safety, tolerability, and effectiveness of SEP-4199 CR 200-400 mg/day in the treatment of subjects with bipolar I depression who previously completed a lead-in study of SEP-4199 CR.

The study will consist of a 12-month open-label flexible-dose treatment period, and a safety follow-up period, as shown in the following figure. There are 15 scheduled visits, including a Baseline visit, 13 visits during the open-label treatment period, and 1 safety follow-up visit 7 (\pm 2) days after the last dose of study drug. If necessary, subjects may return to the clinic at any time for an unscheduled visit.

Note: All subjects are to take SEP-4199 CR 200 mg beginning on Day 1, the day following Baseline (Visit 1E). Abbreviations: BL = Baseline; CR = controlled release; EOT = end of treatmentV = visit; E = extension; W = Week; M = Month

Baseline (Visit 1E; Day -1)

Visit 6/End of Treatment (EOT) (Day 42) of the lead-in study of SEP-4199 CR will serve as the Baseline visit of the current open-label extension study. Subjects who completed 6 weeks of double-blind treatment in a lead-in study of SEP-4199 CR and who meet eligibility criteria to continue into the current extension study may be enrolled. Baseline values for safety and

effectiveness measures for this study will be carried over from Visit 6/EOT (Day 42) of the lead-in study of SEP-4199 CR for each subject. Subjects should continue dosing with SEP-4199 CR in the current open-label study without dosing interruption.

Open-Label Treatment Period (Day 1 to Visit14E/Month 12)

Subjects will self-administer the study drug on an outpatient basis once daily beginning on Day 1 and continue for 12 months. Subjects will be instructed to administer study drug as a single oral dose in the morning at approximately the same time each day. The last dose of study drug will be self-administered by the subject at home on the morning of Visit 14E (Month 12).

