During the open-label treatment period, subjects will have clinic visits at Week 2/Day 14 and Months 1 to 12. In order to facilitate scheduling of clinic visits and telephone calls, a window of ± 2 days will be allowed for Visits 2E (Week 2/Day 14) and 3E (Month 1); a window of ± 5 days will be allowed for Visits 4E (Month 2) to 13E (Month 11), and a window of ± 5 days will be allowed for Visit 14E (Month 12). Between study visits, subjects will be contacted weekly by telephone.

All subjects will initiate treatment with SEP-4199 CR 200 mg/day. The dose may be increased to 400 mg/day at Visit 2E (Week 2/Day 14) or later, based on the Investigator's judgment. However, if clinically indicated, the dose may be increased as early as Day 7 at an unscheduled visit. The dose may be decreased to 200 mg/day at any time thereafter for tolerability. If a dose decrease is needed between study visits, subjects will return to the clinic for an unscheduled visit for drug dispensation. Dose increases will occur only at scheduled or unscheduled clinic visits. Prior to a dose increase, safety assessments will be completed, including but not limited to evaluation of AEs, concomitant medications, vital signs, and ECGs. Subjects whose ECG results, based on machine reading, show increase from Baseline in QT interval corrected for heart rate using Fridericia's formula (QTcF) interval \geq 30 milliseconds (msec) or whose QTcF interval is \geq 480 msec at the 200 mg/day dose are not allowed to have their dose increased to 400 mg/day. Subjects with hyperprolactinemia-related AESI are not allowed to have their dose increased to 400 mg/day.

End of Treatment (EOT)/Early Termination (ET) (Visit 14E: Month 12)

Subjects will have Visit 14E at Month 12 (+ 5 days) for EOT assessments of safety and effectiveness.

Subjects who prematurely discontinue from the study will undergo an ET visit to include all Visit 14E assessments and procedures.

Follow-up Period (Visit 15E, 7 [± 2] days after last dose)

All subjects will have a follow-up visit for safety and tolerability assessments 7 (\pm 2) days after their last dose of study drug. Assessment of potential withdrawal effects will also be made during the follow-up period.

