11.6.1. Visit 1E: Baseline (Day -1)

The Open-Label Baseline visit of the present study is on the same day as Visit 6/EOT (Day 42) in the lead-in study of SEP-4199 CR. Subjects will be evaluated at this visit to determine their eligibility for the study. The following study-related procedures will be performed at Visit 1E; it is suggested that they be performed in the order presented below, as is possible by the site:

- Obtain informed consent, including signed informed consent for duplicate subject check (where local regulations allow).
- Review inclusion and exclusion criteria.
- Record subject demographics.
- Review concomitant medications. Medications taken during the lead-in study of SEP-4199 CR that are ongoing at the start of the current extension study will be entered into the eCRF.
- Record adverse events. Adverse events with onset during the lead-in study of SEP-4199 CR and ongoing at the start of the current extension study will be entered into the eCRF.
- Dispense study drug. Instruct the subject to administer study drug as a single oral dose in the morning at approximately the same time each day beginning the following day (Day 1).
- Schedule next visit:
 - Instruct subject to administer the morning dose prior to the clinic visit. Clinic visits are to begin no later than 6 hours postdose, if possible.
 - Instruct subject to record the date and time of last 3 doses prior to next visit and to bring back all used/unused study drug and packaging to the next visit.
- Schedule weekly telephone check-in with subject.

The following procedures conducted at Visit 6/EOT (Day 42) of the lead-in study of SEP-4199 CR do not need to be repeated for the Open-Label Baseline visit of this study:

• Physical and neurological examinations

- Vital sign measurements
- Weight
- Waist circumference
- 12-lead ECG
- Blood samples for the following laboratory tests (Subjects must have fasted for at least 8 hours.):
 - Hematology and Serum Chemistry
 - Thyroid Panel
 - Serum Prolactin
 - HbA1c
 - Lipid Panel
 - Serum Insulin
 - High-sensitivity C-Reactive Protein (hs-CRP)
- Blood sample for measurement of plasma concentrations of aramisulpride, esamisulpride, and prolactin.
- Urine sample for rapid urine drug test, urinalysis, and urine pregnancy test (human chorionic gonadotropin [β-hCG], female subjects of childbearing potential)
- MADRS
- HAM-A
- YMRS
- QIDS-SR16
- SDS
- EQ-5D-5L
- SHAPS
- CGI-BP-S
- C-SSRS
- AIMS
- BARS
- SAS

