13. TERMINATION OF SUBJECT FROM STUDY/DISCONTINUATION OF STUDY DRUG

13.1. Criteria for Subject Termination

Subjects may terminate the study participation at any time for any reason.

The possible reasons for the termination of study participation are as follows:

- Adverse event
- Lack of efficacy (specify)
- Lost to follow-up (specify)
- Pregnancy
- Withdrawal of consent (specify)
- Non-compliance with study drug (specify)
- Protocol deviation (specify)
- Death
- Other (specify)

If at any time during the course of the study, in the opinion of the Investigator, the subject may no longer safely participate due to a change in medical status (eg, experiences an AE, becomes pregnant), the subject must be discontinued from the study.

Discontinuation due to AE with follow-up until resolution is mandatory in the following cases:

- Subject who, at any study visit post-Baseline, has a QTcF interval > 500 msec, or who has a ≥ 60 msec increase in QTcF from Baseline (machine reading or centrally overread report), or who experiences a life-threatening cardiac arrhythmia must be discontinued from the study, referred to the Investigator for follow-up evaluation, and followed until the event resolves; in addition, an associated AE must be reported.
- Subject who develops an AE of amenorrhea (missed menses for a minimum of 3 months), symptomatic gynecomastia, or galactorrhea that does not resolve within 2 weeks of study drug interruption or that recurs with re-challenge must be discontinued from the study, referred to the Investigator for follow-up evaluation, and followed until the event resolves.
- Subject who answers "yes" to "suicidal ideation" item 4 (active suicidal ideation with some intent to act, without specific plan) or item 5 (active suicidal ideation with specific plan and intent) on any post-Baseline C-SSRS assessment must be discontinued from the study, referred to the Investigator for follow-up evaluation, and followed until the event resolves; in addition, an associated AE must be reported.
- Subjects who require hospitalization/prolonged hospitalization for treatment of COVID-19-related illness will be discontinued. Subjects with an active COVID-19 infection should be discussed on a case-by-case basis with the IQVIA Medical

Monitor to obtain agreement on whether a subject with an active COVID-19 infection should be discontinued.

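### The ≥ 30 msec QTcF block on increasing to 400 mg/day is measured from lead-in Visit 6, so for lead-in 200 mg rollovers it compares 200 mg with 200 mg and misses a rise already present at entry

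*Protocol*

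**What the plan says.** **Dose block.** Protocol 10.1.1 forbids an increase to 400 mg/day for subjects whose ECGs, "based on machine reading, show increase from Baseline in QTcF interval", reach 30 msec or more, or whose QTcF is 480 msec or more at 200 mg/day. Section 7.1 repeats the rule ("show increase from Baseline in QT interval corrected for heart rate using" Fridericia's formula), as does the Synopsis. None of the three says which Baseline is meant.

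**Reference ECG.** Section 7.1 and the Synopsis make lead-in Visit 6/EOT (Day 42) the Baseline visit of this study and carry its safety values over. Section 11.6.1 lists the 12-lead ECG among procedures that "do not need to be repeated for the Open-Label Baseline visit of this study". Where the protocol means the pretreatment value it names it: exclusion 6 in 8.2 counts "msec from Baseline of the lead-in study of SEP-4199 CR AND a QTcF interval" of 480 msec or more.

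**Dosing.** The lead-in arms were 200 mg/day, 400 mg/day and placebo (7.3.2). In the extension, "All subjects will initiate treatment with SEP-4199 CR 200 mg/day", and "Subjects should continue dosing with SEP-4199 CR in the current open-label study without dosing interruption" (7.1).

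**Stop rule.** Section 13.1 discontinues a subject with QTcF above 500 msec, or who "has a ≥ 60 msec increase in QTcF from Baseline (machine reading or centrally overread report"). It uses the same unqualified reference.

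**Reporting.** SAP 18.3.1 counts QTc increases from both the DB Baseline and the OL Baseline, and SAP 18.3 plans a listing of subjects who meet any QTc prolongation criterion.

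**The concern.** The block should keep QTcF-sensitive subjects from moving to 400 mg/day, and for that it has to register what 200 mg/day has done to them. In a placebo rollover it does, because Visit 6 is off drug and Week 2 is on 200 mg. In a lead-in 200 mg rollover both ECGs are on 200 mg, so the drug effect cancels and the change rule responds mainly to ECG variation. Two subjects with similar sensitivity can get opposite decisions depending on lead-in arm, and the one let through goes on to a first exposure to 400 mg.

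Lead-in 400 mg rollovers concern us less. Their reference ECG was taken on 400 mg, so the change rule is numerically weaker still, but they have already taken 400 mg for six weeks and passed exclusion 6 on it.

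What is at stake is the safety of individual subjects during titration.

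**Working it through.** **Step 1. What can enter.** Exclusion 6 removes a rise of ≥ 60 msec from the lead-in Baseline, a rise of ≥ 30 msec with QTcF ≥ 480, and QTcF > 500. In whole milliseconds, the largest rise that passes numerically is 59, and it needs a Visit 6 value of 479 or less.

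**Step 2. What the block then does** (QTcF in msec: lead-in Baseline / Visit 6 / check on 200 mg).

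| Subject | Values | Change from Visit 6 | Change from lead-in Baseline | Rule as written |
|---|---|---|---|---|
| Lead-in 200 mg | 400 / 445 / 445 | 0 | +45 | increase allowed |
| Placebo | 400 / 400 / 430 | +30 | +30 | barred |
| Extreme case | 391 / 450 / 479 | +29 | +88 | increase allowed |
| Fall at Visit 6 | 420 / 400 / 440 | +40 | +20 | barred |

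The last row shows why Visit 6 should not simply be replaced by the lead-in Baseline: that subject would lose a protection now in place.

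**Step 3. How often.** The documents give no QTcF effect or variability for the CR tablet, so everything in this step is assumed: mean 200 mg effect m = 5, 10 or 20 msec; between-subject SD of the effect 5; single-ECG SD w = 8 or 12; normal distributions; one check.

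- Lead-in 200 mg: change from Visit 6 ~ N(0, 2w²); change from lead-in Baseline ~ N(m, 2w² + 25); covariance w².
- Placebo: both changes ~ N(m, 2w² + 25); covariance 25 + w².
- P(either ≥ 30) = 1 − bivariate normal CDF at (30, 30).

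Worked case, w = 8 and m = 10. From Visit 6 the SD is √128 = 11.31, and P(Z ≥ 30/11.31 = 2.65) = 0.4%. From the lead-in Baseline the SD is √153 = 12.37, and P(Z ≥ 20/12.37 = 1.62) = 5.3%. Either: 5.5% for lead-in 200 mg and 9.0% for placebo.

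Percent blocked per check, for m = 5 / 10 / 20:

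| Group | w | Visit 6 (as written) | Lead-in Baseline | Larger of the two |
|---|---|---|---|---|
| Lead-in 200 mg | 8 | 0.4 (any m) | 2.2 / 5.3 / 20.9 | 2.5 / 5.5 / 21.1 |
| Lead-in 200 mg | 12 | 3.9 (any m) | 7.9 / 12.9 / 28.6 | 10.4 / 15.0 / 29.7 |
| Placebo | 8 | 2.2 / 5.3 / 20.9 | same as Visit 6 | 3.8 / 9.0 / 31.6 |
| Placebo | 12 | 7.9 / 12.9 / 28.6 | same as Visit 6 | 13.3 / 20.9 / 42.0 |

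With 64 enrolled (SAP 4.4) and equal lead-in arms assumed, each group has 64/3 = 21.3 subjects. The larger-of-two rule then adds 0.4 to 5.5 blocks per check in lead-in 200 mg rollovers and 0.4 to 2.9 in placebo rollovers. At m = 10 and w = 8 that is 21.3 × (5.54 − 0.40)% = 1.1 and 21.3 × (8.99 − 5.29)% = 0.8. The top end needs a 20 msec mean effect, which no document supports.

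A simulation that adds exclusion 6 and the ≥ 480 limit (true QTcF mean 410, SD 18; 400 mg effect double the 200 mg effect; all assumed) puts lead-in 400 mg rollovers at about 0.1 to 2.5% as written and roughly 2 to 23% under the larger of the two.

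**Step 4. The 60 msec stop.** At one 200 mg check in lead-in 200 mg rollovers, crossing 60 msec is rare: at most 0.02% from Visit 6 and 1.2% from either reference. But 13.1 applies at every post-Baseline visit, and an ECG is scheduled at all 13 treatment visits. Over 13 ECGs on 200 mg, at m = 20 and w = 12, with exclusion 6 and the > 500 stop included, stops rise from 0.7% to 8.5% (lead-in 200 mg) and from 9.1% to 15.7% (placebo). At m = 5 and w = 8 they are 0.01 to 0.02% either way.

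**The case against.** **Which Baseline is meant.** Protocol 15.4 makes the pretreatment lead-in value the default reference for reported changes. Section 15.4.3.4 speaks of QTc changes from an unqualified Baseline, which the SAP applies to both references. One could argue that 10.1.1 is merely ambiguous. Those sections govern reporting, however. For conduct, 7.1 defines the Baseline visit, 11.6.1 carries its ECG over, and exclusion 6 names the other Baseline when it wants it. Visit 6 is the reading a site would follow.

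**Other safeguards.** A reader might infer that subjects with a rise of 30 to 59 msec enter automatically and then meet no check. The documents do not support that. Exclusion 6 also bars a treatment-emergent clinically significant ECG abnormality, inclusion 3 requires medical suitability, and 12.2 removes subjects with a clinically significant ECG at Visit 1E and mandates discontinuation for later ones. Appendix I has the investigator review ECGs for change from previous assessments, the DSMB reviews safety data, and the ≥ 480 limit needs no reference value. All of this stands and narrows the gap. The clinical safeguards rest on judgment, though, and the 480 limit cannot detect a large rise from a low starting value.

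**Reach and size.** The SAP reports early termination with 64 enrolled (4.4, 4.7), so new protocol wording may protect few or none. Protocol 4.3 reports substantially less QTc prolongation with CR than with IR. Both points stand and hold the severity down.

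**Cost to others.** Two references give two chances to cross 30 msec by noise, including in placebo rollovers, for whom the rule already works, and in lead-in 400 mg rollovers, for whom it bars a return to a dose already taken. This is a real cost. It is acceptable for the dose block because a blocked subject stays on 200 mg/day, a permitted dose.

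**Conclusion.** The point holds for the dose-increase block. For lead-in 200 mg rollovers the ≥ 30 msec rule does not count a rise already present at entry, numerically up to 59 msec when QTcF is below 480. This follows from the text alone. How many subjects it touches is unknown, and the percentages above illustrate assumed effects and variability.

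A reader might infer that the ≥ 60 msec stop in 13.1 should change in the same way at negligible cost. It shares the reference, but that does not follow. Counted over all scheduled ECGs, the added stops can be substantial at the top of the assumed range. The change would also sit awkwardly with eligibility: a subject at 400 then 455 may enter numerically and would have to stop at 460, 5 msec above entry. Whether to change the stop is a separate clinical choice.

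Nor do the documents support a reading that results are distorted, since the SAP reports QTc changes from both baselines. Severity is minor: subject safety only, with no effect on the trial's conclusions.

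**What to change.** 1. In Protocol 10.1.1, 7.1 and the Synopsis, apply the ≥ 30 msec dose block to the QTcF increase from the lead-in study Baseline or from Visit 6, whichever is larger. Keep the ≥ 480 msec limit. Apply it to all subjects, because the lead-in may still be blinded and sites cannot tell the arms apart.
2. Leave the ≥ 60 msec stop in 13.1 as it is unless the clinical team decides otherwise after counting added stops over all scheduled ECGs and in all three rollover groups. Either way, state which Baseline it uses.
3. Because rewording may come too late for the 64 enrolled, flag in the QTc listing planned in SAP 18.3 the subjects who met a threshold from DB Baseline but not from OL Baseline, and show any later 400 mg/day dosing.

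The cost is three wording edits to the dose block, a clarification of the reference in 13.1, and one flag in a listing already planned. No new ECGs are needed, and sites already compute the rise from the lead-in Baseline on machine readings for exclusion 6. The downside is that more subjects stay at 200 mg/day, some because of ECG noise: for example, placebo rollovers go from 5.3% to 9.0% per check at a 10 msec mean effect and SD 8, and lead-in 400 mg rollovers also rise.
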